### **3 STUDY DESIGN**

- Type: non-randomized, single arm, phase IV, cohort pilot study
- Study population: end stage renal disease patients who are on chronic hemodialysis or peritoneal dialysis with elevated serum phosphorus.
- 55 chronic dialysis patients (28 hemodialysis and 27 peritoneal dialysis) who are currently using oral phosphorus binders will be enrolled. Potential participants will be screened from both the chronic hemodialysis unit and the home dialysis unit at the LAMC site. Potential study patients will be approached by study investigators during any routine visit. If the patient consents to participation, the study coordinator will see patients during the same visit. If study staff is unable to meet with patient during routine visit or if the patient requests more time to consider participation, peritoneal dialysis patients may be asked to return to clinic for an additional visit to sign the informed consent. This will only apply to peritoneal dialysis patients. If the patient chooses not to enter the study, the reason will be noted by the study coordinator. At the appropriate time in the study, the study coordinator will dispense the study medication, Ferric Citrate, and provide instructions per study protocol. The study coordinator will meet with the participant every month during either a hemodialysis visit (for hemodialysis patients) or a monthly clinic visit (for peritoneal dialysis patients) with his/her provider, and laboratory values/data and study questionnaire will be updated each month. If at any time during the study, a peritoneal, dialysis patient changes to hemodialysis, the patient can continue study at the principal investigator's discretion. If at any time during the study, a hemodialysis patient changes dialysis to peritoneal, the patient can continue on study at the principal investigator's discretion. In such event, patient's group assignment for analysis will be determined at the discretion of the Principal Investigator. Patients will be allowed to continue in the trial given that they can continue to meet all study participation requirements. The six month period prior to enrollment will be used to evaluate the

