participants' baseline laboratory values and medication use, including phosphorus binder use. Laboratory values and medication use will also be evaluated and recorded monthly during the six months of active study. The duration of the study will be six months on ferric citrate. At the end of the study, the participant can be provided with a prescription of ferric citrate by his/her nephrologist if the participant wishes to continue with ferric citrate, or he/she can go back to the phosphorus binder used before enrolling in this study.

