#### 3.1 Treatment Arms

This is a single arm study in which all participants will be changed to the study medication for a total of six months.

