### **5** SELECTION AND WITHDRAWAL OF PATIENTS

#### 5.1 Inclusion Criteria

- 5.1.1 Currently using 3 + pills per day of calcium acetate, sevelamer, lanthanum, or calcium carbonate
- 5.1.2 Mean serum phosphorus 4.0-<8.0 mg/dl for 6 months prior to enrollment
- 5.1.3 No allergy to iron
- 5.1.4 Mean corrected serum calcium > 8.0 mg/dl for 6 months prior to enrollment
- 5.1.5 Mean PTH < 1000 pg/ml for 6 months prior to enrollment
- 5.1.6 Mean ferritin < 1500 ng/ml and mean iron sat < 50% for 6 months prior to enrollment
- 5.2 Exclusion Criteria
  - 5.2.1 History of gastrointestinal bleeding within past 6 months
  - 5.2.2 History of hospitalization for gastroparesis, bowel obstruction, or abdominal surgery within past 6 months
  - 5.2.3 Acute kidney injury equal to or less than 3 months before the initial screening date
  - 5.2.4 Active malignancy
  - 5.2.5 Functioning renal transplant
  - 5.2.6 Patients with iron overload syndrome (e.g., Hemochromatosis)
  - 5.2.7 History autoimmune disease, hemoglobinopathy, hemochromatosis, sickle cell disease
  - 5.2.8 Active or past history of calciphylaxis

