### 8.3.2 Serious Adverse Event Reporting

SERIOUS ADVERSE EVENT (SAE) is an adverse event or suspected adverse reaction if, in the view the study investigator, it meets one or more of the following criteria:

- Results in death
- Is a life-threatening adverse event (places the subject at immediate risk of death from the event as it occurred)
- Results in inpatient hospitalization or prolongation of existing hospitalization
- Results in a persistent or significant incapacity or substantial disruption of the ability to conduct normal life functions
- An important medical event that may not result in death, be lifethreatening, or require hospitalization may be considered serious when, based upon appropriate medical judgment, the event may jeopardize the patient and may require medical or surgical intervention to prevent one of the outcomes listed in this definition

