### 10.2 Secondary Endpoints

- i. Total cumulative and average weekly dose, number of doses of iv iron administered before and after treatment with ferric citrate
- ii. Total ESA dose and mean weekly dose administered 6 months before and after ferric citrate treatment
- Total dose of ferric citrate and average number of pills/day required to maintain phosphorus control compared to previous dose and pill burden with binder
- iv. Compare serious adverse events including tolerability of ferric citrate compared to previous binder

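### Secondary endpoint 10.2 iv compares serious adverse events with the previous binder, but eligibility and survival empty the six-month baseline of several event types, and the look-back for other events is undefined

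*Combined protocol and SAP*

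**What the plan says.** Section 10.2 iv is worded as a comparison: "Compare serious adverse events including tolerability of ferric citrate compared to previous binder". Section 3.1 says "This is a single arm study in which all participants will be changed to the study medication", so there is no concurrent control. Item iv gives no window, unit of count or estimator, and section 14.4 (Final Analysis Plan) is marked not applicable.

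The one period before treatment that the protocol defines is in section 3: "The six month period prior to enrollment will be used to evaluate the" participants' "baseline laboratory values and medication use, including phosphorus binder use". Sections 10.1 and 10.2 ii also use six months before and after.

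Two exclusions cover a period of the same length. Item 5.2.1 is "History of gastrointestinal bleeding within past 6 months" and item 5.2.2 is "History of hospitalization for gastroparesis, bowel obstruction, or abdominal surgery within past 6 months". Neither states the date from which the six months run back.

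On treatment, section 8.3.2 makes death a criterion for a serious adverse event, together with an event that "Results in inpatient hospitalization or prolongation of existing hospitalization". Section 9.2 asks about hospitalizations of any kind and about GI bleeding.

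For collection at baseline, section 9.1.2 lists IV iron and ESA use, laboratory values and medication use over the previous six months, but no adverse events. The study calendar (9.4) ticks an adverse event assessment under baseline data, and 9.1.1 takes a history from the record and the patient. No look-back, event list or method is given for either. Section 8.3.3 (Notifying FDA) starts monitoring of serious events at consent. On drug, section 8.1 has the coordinator screen for side effects every one to two weeks. Section 5.3 ends participation for any serious adverse event.

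**The concern.** A comparison of each patient with his or her own past is fair only if the event could have been counted in both periods and was looked for in the same way. Here neither condition is secured.

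Some event types are screened out of the earlier period by the entry rules but counted in the later one. A table of zero before and some after would then arise from eligibility alone. With no analysis plan to qualify it, it could be read as harm from ferric citrate. For the remaining serious events, the text does not say how far back, from what source or by what definition the earlier period is to be searched.

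Tolerability has a selection problem too. Entry requires current use of at least three "pills per day of calcium acetate, sevelamer, lanthanum, or calcium carbonate", which leaves out patients who had already stopped their binder. Opt-in recruitment (9.1.1) may attract those unhappy with it. These pull in opposite directions, so the net effect on a tolerability comparison is uncertain.

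**Working it through.** The plan gives no event rate, power or sample-size derivation (14.2 and 14.4 are not applicable), so there is no figure to reproduce. The check is first logical, then illustrative.

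**Step 1. What each period can contain, if the six months before enrollment are used.**

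| Event type | Before | On ferric citrate |
|---|---|---|
| Death | None: the patient must be alive to consent | Serious event (8.3.2) |
| GI bleeding | None or nearly none (5.2.1) | Asked about (9.2); serious if it meets 8.3.2 |
| Admission for gastroparesis, bowel obstruction or abdominal surgery | None or nearly none (5.2.2) | Serious event (8.3.2); admissions asked about (9.2) |
| Other serious events, such as infection or heart failure | Possible; search undefined | Screened every one to two weeks (8.1) |

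The zero is exact for deaths. For the other two rows it is exact only if the exclusion look-back and the baseline window run back from the same date. If the exclusion runs back from screening and the baseline from a later date, an event in between could be counted before.

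**Step 2. Size for the affected types, as an illustration.** Inputs: n = 55 (section 3); p = combined six-month risk of all affected types, assumed equal in both periods; complete follow-up. With the before count taken as zero:

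P(after > before) = 1 − (1 − p)^n, and P(before > after) = 0.

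| Assumed p | Expected patients after (55p) | 1 − (1 − p)^55 |
|---|---|---|
| 1% | 0.55 | 1 − 0.575 = 42% |
| 2% | 1.1 | 1 − 0.329 = 67% |
| 5% | 2.75 | 1 − 0.060 = 94% |
| 10% | 5.5 | 1 − 0.003 = 99.7% |

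If follow-up amounts to 44 patients (an assumed 80% of 55), the 2% and 5% rows become 1 − 0.98^44 = 59% and 1 − 0.95^44 = 90%.

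**Step 3. Benchmark.** If the events could be counted in both windows, with independent Binomial(55, p) counts, each direction would have probability 35% at p = 2% and 41% at p = 5%. This benchmark has meaning only for the non-fatal types, because a death can never fall in the earlier window.

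**Step 4. Would a test be misled?** An exact two-sided McNemar test of 0 against k patients gives 2 × 0.5^k: 0.0625 at k = 5 and 0.031 at k = 6. With no true difference, the chance of 6 or more of 55 is 0.1% at p = 2%, 5.6% at 5% and 48% at 10%. At low risks the distortion therefore lies in the descriptive table rather than in a significance test.

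**Step 5. Other serious events.** Over 26 weeks, screening every one to two weeks gives 26/2 = 13 to 26 scheduled contacts, against one baseline assessment of unstated scope. This can raise the on-drug count. Section 5.3 works the other way: participation ends at a serious event, so on-drug observation is cut short and repeat events may be missed. The documents do not allow the two effects to be weighed.

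**The case against.** The strongest reply is that the six-month window is inferred. Item iv does not state it, although item ii in the same list does, and section 3 ties that period to laboratory values and medication use. This stands: the empty cells are a consequence of that window. A longer look-back could contain earlier bleeds and listed admissions, though never a death. But the protocol offers no other window, and leaving it open is itself a gap.

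Second, the exclusions carry no anchor date, unlike 5.2.3, so the non-fatal zeros may not be exact. This also stands and is why the claim says nearly all.

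Third, admissions and deaths are largely record events, electronic records are a named source (12.1), and counting contacts does not measure completeness. This has force. A reader might infer that closer questioning must inflate the on-drug count of all serious events. The documents do not support that, given the record source and the opposite pull of 5.3.

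A reader might also infer that no baseline adverse events are collected. The calendar ticks an assessment, and the data collection form (Appendix III) is not reproduced and may hold event fields. The supportable statement is that the text does not define the search.

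Finally, this is a pilot that the summary describes as not powered for significance, and no test is planned. That limits the consequence but does not remove it: the fault is bias, and a descriptive before/after table carries it without any test.

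**Conclusion.** The concern holds in a limited form. If the comparison in 10.2 iv uses the protocol's only defined earlier window, deaths are absent from it by necessity, and GI bleeds and the 5.2.2 admissions are absent or nearly so. For these types the contrast runs essentially one way whatever the true risk. The 67% and 94% chances of an apparent excess rest on assumed risks of 2% and 5%, equal risk in both periods and full follow-up; the direction does not depend on those figures, but it does depend on the inferred window. The expected excess is small in number, 1.1 or 2.75 patients of 55.

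For other serious events the comparison is undefined and its net bias uncertain. The reading that the plan will overstate all serious events on ferric citrate goes further than the documents allow, as does the reading that on-drug safety reporting is unsound. The point affects the comparison in one secondary endpoint. It should be corrected because the remedy is cheap and nothing in section 14 would catch the problem later.

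**What to change.** In 10.2 iv, drop the comparative claim for serious adverse events. Report the proportion of patients with at least one such event on ferric citrate, with an exact 95% confidence interval.

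Report discontinuations for an adverse event separately by reason: patient or investigator choice for intolerance, against exit required by the protocol after a serious event. Otherwise the figure partly reflects the exit rule rather than tolerability. Section 5.3 (any serious adverse event) and section 7.2.2 (events attributable or possibly attributable to the drug) differ on when a patient leaves, and must be reconciled.

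Describe tolerability and the binder preference recorded at the final visit without a comparison. State the look-back, event list and source for the baseline adverse event assessment, so that 9.1.2 agrees with the calendar.

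If a before/after contrast is kept:

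- limit its serious-event part to hospitalizations taken from the electronic record by one definition;
- use equal six-month windows, with the earlier one anchored to the same date as the 5.2.1 and 5.2.2 look-back;
- omit deaths and the 5.2.1 and 5.2.2 event types from both sides;
- count the later window to month 6 even if participation ends early, unless consent is withdrawn;
- state that survival and current binder use were conditions of entry.

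Cost: the comparative claim is lost or narrowed, and the change must go to the IRB (17.1). A retained contrast needs a short record extraction for 55 patients, which may miss admissions outside the health system.

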4.6 Toxicity and Safety Information

Patients with iron overload syndromes (e.g., hemochromatosis) are contraindicated to take Ferric Citrate, as the iron absorption may lead to excessive elevation in iron stores. Iron levels in blood will be monitored closely on a monthly basis. Accidental overdose of iron-containing products is a leading cause of fatal poisoning in children under 6 years of age, therefore no children are included in this study. Patients with inflammatory bowel disease or active, symptomatic gastrointestinal bleeding were excluded from clinical trials, therefore these populations are excluded from this current study.

In clinical trials, adverse events reported in more than 5% of patients treated with Ferric Citrate, at a rate similar to the control group. Side effects reported included diarrhea (21%), nausea (11%), constipation (8%), vomiting (7%), and cough (6%4) as per the package insert. Gastrointestinal adverse reactions were the most common reason for discontinuing Ferric Citrate. The study medication is also associated with discolored feces.

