### 8 ASSESSMENT OF EFFICACY AND SAFETY

### 8.1 Toxicity Monitoring

Laboratory monitoring will occur on a bi-monthly basis for the first two months, then on a monthly basis and as needed. Laboratories monitored will include

Page 19 of 35

calcium, phosphorus, iron levels, ferritin, and complete blood count. In addition, participants will be screened by the study coordinator either in person or via the phone every week to two weeks on adverse side effect monitoring.

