### 8.3.1 Definitions

Adverse Event (AE) is any untoward medical occurrence associated with the use of a drug in humans, whether or not considered drug related.

All adverse events, including those that are reported by the patient spontaneously, those the study investigator observes, and those that the study investigator elicits in response to open-ended questions. Recorded adverse events will be assessed by the study investigator indicating the causal relationship of the event with the study drug and whether it meets the criteria for a Serious Adverse Event.

Some reported adverse drug reactions include diarrhea, constipation, abdominal discomfort, abdominal distension, duodenal ulcer, and nausea.

Serious Adverse Event noted in prior publications included death, duodenal ulcer, congestive heart failure, dialysis access shunt stenosis, and infections.

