### 8.3.3 Time Period and Frequency for Event Assessment and Follow-up

Adverse events are collected on a weekly basis for the in center hemodialysis patients, and on a bi-monthly basis from the home dialysis patients, and again 30days after the termination of the study.

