### 9.1.2 Recording of baseline data

A baseline assessment of patient's compliance with usual medications will be performed.

The study coordinator will then review previously obtained routine monthly laboratory values from the dialysis unit, including complete blood count, iron saturation, ferritin, phosphorus, calcium, parathyroid hormone (a total of 6 months of previous data to be reviewed). The study coordinator will then use this baseline data to help determine a patient's eligibility for participation in the active portion of the study, based on the criteria listed in section 5.1. After it is determined that patient actually qualifies for participation in the study, the following will be recorded by the study coordinator:

- Patient's average weekly IV iron and erythropoiesis stimulating agent use (6 months of retrospective data)
- 6 months of retrospective routine laboratory data (CBC, iron saturation, ferritin, calcium, phosphorus, albumin, intact parathyroid hormone levels) will be recorded for each of the previous 6 calendar months
- 6 months of retrospective data regarding medication use will be recorded for each of the previous 6 calendar months (including calcitriol or other vitamin D analogs, cinacalcet, and phosphorus binders), including frequency and dose

After baseline data is obtained, participants will be dispensed a 1 month supply of the study medication, with the starting dose of 1-2 tablets per meal, three times a day. This will mark the start of the active study drug phase.

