#### 9.2 Clinical Evaluations

**Laboratory testing will include**: complete blood count, iron saturation, ferritin, phosphorus, calcium, parathyroid hormone, and aluminum level

**Symptoms evaluation will include**: any hospitalizations, infections, GI bleed, dialysis access complications, diarrhea, constipation, abdominal discomfort, abdominal distension, duodenal ulcer, nausea, and stool color changes.

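### Secondary endpoint 10.2 iv compares tolerability with the previous binder, but side effects are sought repeatedly on ferric citrate and at most once, in an undefined way, before the switch

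*Combined protocol and SAP*

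**What the plan says.** Section 10.2, item iv, sets the comparison: "Compare serious adverse events including tolerability of ferric citrate compared to previous binder". It names no time window, metric or test, and section 14.4 (Final Analysis Plan) is marked not applicable.

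**On ferric citrate.** The second of the two sections numbered 8.3.3 (Time Period and Frequency) states: "Adverse events are collected on a weekly basis for the in center hemodialysis patients, and on a bi-monthly basis from the home dialysis patients". Section 8.1 has the coordinator in contact "every week to two weeks on adverse side effect monitoring". Sections 9.1.3 and 9.1.4 (Final Visit) add adverse event assessments at V1 to V5 and at V6. Section 8.3.1 counts spontaneous reports, observed events and "those that the study investigator elicits in response to open-ended questions". Section 9.2 lists symptoms to evaluate, including "diarrhea, constipation, abdominal discomfort, abdominal distension, duodenal ulcer, nausea, and stool color changes", but does not say at which contacts the list is used.

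**On the previous binder.** Section 3 uses the six months before enrollment for laboratory values and medication use. Section 9.1.2 itemizes laboratory results, IV iron, ESA and drugs ("6 months of retrospective data regarding medication use will be recorded for each of the previous 6 calendar months"), plus a compliance assessment. It mentions no symptoms, adverse events or hospitalizations. The section 9.4 calendar does tick an adverse event assessment in its baseline column, without recall period, method or instrument. Section 8.3.3 (Notifying FDA) starts serious-event monitoring at consent.

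**The concern.** A before/after comparison of side effects is interpretable only if events had a similar chance of being recorded in both periods. Mild diarrhea, nausea or constipation is recorded mainly when somebody asks. Here patients are asked many times in one period and at most once, in an unstated way, in the other. If ferric citrate and the previous binder were equally well tolerated, following the plan as written would tend to show ferric citrate as worse.

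The serious-event half has a related gap. Nearly all of the previous-binder period precedes consent, so it lies outside the monitoring window, and no section says that earlier serious events will be retrieved.

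What is at stake is the answer to item iv: a difference could not be attributed to the drug rather than to the frequency of asking. Section 14 says the study aims to identify real-world difficulties in switching binders, so readers are likely to look at this comparison.

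**Working it through.** The plan states no effect size, power or analysis for item iv, so there is no figure to reproduce. The check is a count of contacts followed by an illustration.

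**Step 1. Opportunities to record a side effect.**
- In-center, on ferric citrate: weekly for six months, 6 × 52/12 = 26 contacts. The six monthly visits (V1 to V6) may coincide with some of these.
- Home, on ferric citrate: about 13 calls if bi-monthly means every two weeks, or 3 if it means every two months, plus the six visits. The first reading fits better: section 8.1 uses bi-monthly for early laboratory tests that section 7.1 schedules every two weeks, and section 8.1 itself has contacts at one- to two-week intervals.
- Previous binder: at most 1, the baseline tick in section 9.4.

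**Step 2. What unequal capture does when true tolerability is equal.**

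Inputs from the documents: N = 55 (section 3); diarrhea 21% on ferric citrate, reported in earlier trials "at a rate similar to the control group" (section 4.6). Assumptions: the 21% applies to each period here (section 4.6 gives no trial duration); capture is 90% on ferric citrate and 90%, 75%, 50% or 25% before.

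Formula: observed proportion = true proportion × capture. On ferric citrate: 0.21 × 0.90 = 18.9%, or 55 × 0.189 = 10.4 patients.

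| Capture before | Observed before | Patients of 55 | Difference (points) | Ratio |
|---|---|---|---|---|
| 90% | 18.9% | 10.4 | 0.0 | 1.0 |
| 75% | 15.8% | 8.7 | 3.1 | 1.2 |
| 50% | 10.5% | 5.8 | 8.4 | 1.8 |
| 25% | 5.2% | 2.9 | 13.7 | 3.6 |

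The ratio is 0.90 divided by the capture before, so it does not depend on the 21%. At 50% capture before, nausea (true 11%) would appear as 9.9% against 5.5%, and constipation (true 8%) as 7.2% against 4.0%.

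**Step 3. Chance of a false finding if the periods were tested.** The plan names no test. With an exact two-sided McNemar test at 0.05 and N = 55, the chance that diarrhea is significantly worse on ferric citrate is:

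| Capture before | Events independent between periods | Same patients affected in both |
|---|---|---|
| 90% | 1.4% | about 0% |
| 75% | 4% | 2% |
| 50% | 16% | 29% |
| 25% | 49% | 73% |

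**Step 4. Other influences.** Section 5.1.1 requires current use of at least three binder pills a day, so people who could not tolerate a binder are under-represented; this pushes the same way. Withdrawals under sections 5.3 and 7.2 shorten time on ferric citrate, which can partly offset the bias in raw counts. Neither is quantified in the documents.

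**The case against.** The strongest reply is that pre-switch symptoms may in fact be collected. The calendar ticks a baseline adverse event assessment before drug is dispensed, a full history is taken at screening, section 3 mentions a monthly questionnaire, and the data collection form is listed only by title. This stands as far as it goes. A reader might infer that side effects are asked about only on ferric citrate, and the calendar contradicts that. But one undescribed assessment does not match repeated contacts over six months.

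Second, item iv does not state a six-month comparison of rates; that window appears in item ii. This also stands. The bias applies to any comparison of counts or rates between periods, and because section 14.4 is empty, nothing in the plan prevents or corrects one. The end-of-study binder preference (section 9.1.4, Final Visit) does not depend on how often events were asked about, but the plan does not link it to item iv.

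Third, the medical record (section 12.1) could supply earlier events. For hospitalizations this is plausible, though no section says it will be done. For mild gastrointestinal symptoms it is a weak substitute for asking. The 30-day follow-up, when some patients may be back on their old binder, is not designated as previous-binder data.

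Fourth, this is a pilot that its summary describes as not powered for significance. That limits the weight of any test, but a descriptive table of unequally ascertained rates misleads just as readily.

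**Conclusion.** The concern holds for secondary endpoint 10.2 iv and should be fixed. A comparison of event counts or rates between the two periods is biased against ferric citrate. The direction follows from the design, provided only that repeated asking captures at least as much as a single assessment. The size is not known: the ratios of 1.2 to 3.6 rest on assumed capture of 90% on ferric citrate and 75% to 25% before.

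Stronger readings are not supported:
- A 2- to 10-fold spurious excess might be inferred by assuming 50% to 10% capture before and complete capture on drug (1/0.50 = 2; 1/0.10 = 10). The documents give neither figure.
- Specific Aim 1 might seem compromised. It concerns tolerability of ferric citrate and names no comparator, so the prospective data can serve it.
- The section 9.2 symptom list might be thought to be used at every contact. The text does not tie it to any contact, and section 8.3.1 speaks of open-ended questions.
- An excess of stool color change would not in itself show this bias, because section 4.6 associates it with the drug.

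The serious-event half is less exposed, since hospitalizations can be retrieved for both periods, but the plan does not yet provide for it.

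**What to change.** 1. **Section 9.1.2.** Reconcile it with the section 9.4 calendar: state that the baseline adverse event assessment asks the section 9.2 symptom list about the current binder over a fixed recall period.
2. **Section 10.2 iv, tolerability.** Compare that answer within patient with the same question and recall period at one pre-specified ferric citrate visit, or the last visit if the patient withdraws. Use one visit, so that each period has one opportunity.
3. **Full ferric citrate experience.** Report the elicited adverse event incidence, including start-up symptoms and discontinuations, descriptively with a confidence interval and no contrast with the previous binder.
4. **Section 10.2 iv, serious events.** Take hospitalizations from the electronic medical record by the same rules in both six-month windows, expressed per patient-month. Report deaths on ferric citrate only, because nobody enrolled can have died in the look-back. The same applies to events that sections 5.2.1 and 5.2.2 exclude in the prior six months (gastrointestinal bleeding; the listed abdominal admissions), which eligibility removes from the earlier window.

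The cost is a few lines in sections 9.1.2 and 10.2 and one record extraction; the symptom list and baseline assessment already exist. The downside is that a single-visit prevalence misses transient symptoms, including start-up symptoms on ferric citrate, and compares people settled on a binder with people who recently switched. It must therefore be read alongside the descriptive incidence in item 3.
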